6. DOSING DELAYS/DOSE MODIFICATIONS

This section provides guidelines for dose modification guidelines and holding parameters for KRT-232 (AMG 232), carfilzomib, lenalidomide, and dexamethasone to manage possible toxicity. There should be no dose modifications of KRT-232 (AMG 232) and KRD during the DLT-evaluable period (Cycle 1). Subjects requiring dose-reductions during the DLT-evaluable period (Cycle 1) will be considered a DLT.

Guidelines on dose-reductions for carfilzomib were based on the Carfilzomib Prescribing Information 2016 (Amgen Inc, 2016).

Guidelines on dose-reduction for lenalidomide were based on the Lenalidomide Prescribing Information 2015 (Celgene Inc, 2015).

6.2. Dose Reductions

KRT-232 (AMG 232)

Dose Level	KRT-232 (AMG 232) Dose
- 1	30 mg/day PO x 7 days out of 28 day cycle
+ 1	60 mg/day PO x 7 days out of 28 day cycle
+ 2	90 mg/day PO x 7 days out of 28 day cycle
+ 3	120 mg/day PO x 7 days out of 28 day cycle
+ 4	180 mg/day PO x 7 days out of 28 day cycle
+5	240 mg/day PO x 7 days out of 28 day cycle

Carfilzomib

Dose Level	Carfilzomib Dose
- 2	15 mg/m ²
- 1	20 mg/m ²
+1	27 mg/m ²

Lenalidomide

Dose Level	Lenalidomide Dose
- 3	5 mg
- 2	10 mg
- 1	15 mg
+1	25 mg

Dexamethasone

Dose Level	Dexamethasone Dose
- 2	12 mg
- 1	20 mg
+ 1	40 mg

6.3. Non-Hematologic Toxicity Dose Delay/Dose Modification Guidelines.

[REDACTED]	[REDACTED]
[REDACTED]	[REDACTED]
[REDACTED]	[REDACTED]

	Management/Next Dose for KRT-232 (AMG 232)

	Management/Next Dose for KRT-232 (AMG 232)

	Management/Next Dose for KRT-232 (AMG 232)

Management/Next Dose for KRT-232 (AMG 232)	
[REDACTED]	[REDACTED]

Acute Renal Injury	Management/Next Dose for Carfilzomib
≤ Grade 1	No change in dose.
≥ Grade 2 or Creatinine clearance < 15 mL/min, or creatinine clearance decreases to less than or equal to 50% of baseline, or need for dialysis	
Withhold dose and continue monitoring renal function (serum creatinine or creatinine clearance)
 
If attributable to carfilzomib, resume when renal function has recovered to within 25% of baseline; start at 1 dose level reduction
 
If not attributable to carfilzomib, dosing may be resumed at the discretion of the physician
 
For subjects on dialysis receiving carfilzomib, the dose is to be administered after the dialysis procedure

*Subjects requiring a delay of > 4 weeks should go off protocol therapy.
 **Subjects requiring > two dose reductions should go off protocol therapy.

Hepatic Impairment	25% dose reduction in case of baseline or treatment emergent mild or moderate hepatic impairment. 
 -Withhold carfilzomib until resolved or returned to baseline. -After resolution, consider if restarting carfilzomib appropriate; may be reinitiated at a reduced dose with frequent monitoring of liver function. -If tolerated, the reduced dose may be escalated to previous dose at the discretion of the physician. -Monitor liver enzymes regularly, regardless of baseline values, and modify dose based on toxicity.
Posterior Reversible Encephalopathy Syndrome (PRES)	
 -If PRES is suspected, hold carfilzomib. Consider evaluation with MRI for onset of symptoms suggest PRES. -If PRES is confirmed, permanently discontinue carfilzomib. -If PRES is excluded, may resume carfilzomib at same dose if clinically appropriate. -If PRES recurs, permanently discontinue carfilzomib
Thrombotic Microangiopathy (TMA)	
 -If TMA is suspected, hold carfilzomib and manage as per standard of care. -If TMA is confirmed and related to carfilzomib, permanently discontinue carfilzomib. -If TMA is excluded, may restart carfilzomib.

- For other ≥ 3 non-hematologic toxicity assessed as KRT-232 (AMG 232)-related, KRT-232 (AMG 232) will be held until toxicity resolves to \leq Grade 1 or baseline. KRT-232 (AMG 232) will be restarted at 1 dose decrement.
- For other ≥ 3 non-hematologic toxicity assessed as carfilzomib-related, carfilzomib will be held until toxicity resolves to \leq Grade 1 or baseline. Consider restarting carfilzomib at 1 dose decrement at physician's discretion.
- For other ≥ 3 non-hematologic toxicity assessed as lenalidomide-related, lenalidomide will be held until toxicity resolves to \leq Grade 2 or baseline. Consider restarting lenalidomide at 1 dose decrement at physician's discretion.

6.4. Hematologic Toxicity Dose Delay/Dose Modification Guidelines.

Neutropenia	Management/Next Dose for KRT-232 (AMG 232)	Management/Next Dose for Carfilzomib
\leq Grade 2	No change in dose.	No change in dose.
Grade 3	Hold treatment. Add colony stimulating factor. ^a Check weekly CBC. Resume at same dose level when until \leq Grade 2. For subsequent grade 3 or 4 neutropenia, restart at 1 dose decrement.	No change in dose.
Grade 4	[REDACTED] [REDACTED] [REDACTED] [REDACTED] [REDACTED] [REDACTED] [REDACTED]	Hold treatment. Add colony stimulating factor. Check weekly CBC. Resume at same dose level when \leq Grade 3. For subsequent grade 4 neutropenia, restart at 1 dose decrement.
*Subjects requiring a delay of > 4 weeks should go off protocol therapy. **Subjects requiring $>$ two dose reductions should go off protocol therapy.		
^a Colony stimulating factors such as filgrastim or sargramostim as examples.		

Neutropenia	Management/Next Dose for Lenalidomide
\leq Grade 2	No change in dose
Grade 3 or 4	Hold treatment. Add colony stimulating factor. ^a Check weekly CBC. Resume at same dose level when \leq Grade 2.

Neutropenia	Management/Next Dose for Lenalidomide
	For subsequent grade 3 or 4 neutropenia, restart at 1 dose decrement.
* Subjects requiring a delay of > 4 weeks should go off protocol therapy.	
** Subjects requiring > two dose reductions should go off protocol therapy.	
^a Colony stimulating factors such as filgrastim or sargramostim as examples.	

Thrombocytopenia	Management/Next Dose for Carfilzomib
$\geq 10,000 \text{ cells/mm}^3$	No change in dose
$< 10,000 \text{ cells/mm}^3$ or bleeding	Hold treatment. Check weekly CBC Resume at same dose level when $\geq 10,000 \text{ cells/mm}^3$ For subsequent thrombocytopenia $< 10,000 \text{ cells/mm}^3$, restart at 1 dose decrement.

Thrombocytopenia	Management/Next Dose for Lenalidomide
≥ 30,000 cells/mm ³	No change in dose
< 30,000 cells/mm ³	Hold until treatment. Check weekly CBC. Hold prophylactic anticoagulation. Restart at 1 dose decrement ≥ 30,000 cells/mm ³

6.5. Dexamethasone Toxicity Dose Delay/Dose Modification Guidelines.

Body System	Symptom	Recommended Action
Gastrointestinal	Dyspepsia, gastric or duodenal ulcer, gastritis Grade 1–2 (requiring medical management)	Treat with H2 blockers, sucralfate, or omeprazole. If symptoms persist despite above measures, decrease dexamethasone dose by 1 dose level.
Gastrointestinal	> Grade 3 (requiring hospitalization or surgery)	Hold dexamethasone until symptoms adequately controlled. Restart dexamethasone at 1 dose decrement along with concurrent therapy with H2 blockers, sucralfate, or omeprazole. If symptoms persist despite above measures,

		discontinue dexamethasone permanently.
Gastrointestinal	Acute pancreatitis	Discontinue dexamethasone permanently.
Cardiovascular	Edema > Grade 3 (limiting function and unresponsive to therapy or anasarca)	Diuretics as needed, and restart dexamethasone at 1 dose decrement; if edema persists despite above measures, decrease dose another level. Discontinue dexamethasone permanently if symptoms persist despite second reduction.
Neurology	Confusion or mood alteration > Grade 2 (interfering with function +/- interfering with activities of daily living)	Hold dexamethasone until symptoms resolve. Restart dexamethasone at 1 dose decrement. If symptoms persist despite above measures, reduce by another dose decrement.
Musculoskeletal	Muscle weakness > Grade 2 (symptomatic and interfering with function +/- interfering with activities of daily living)	Decrease dexamethasone by 1 dose level. If weakness persists, decrease dose by 1 more dose level. Discontinue dexamethasone permanently if symptoms persist.
Metabolic	Hyperglycemia \geq Grade 3	Treatment with insulin or other hypoglycemic agents as needed. If uncontrolled despite above measures, decrease dose by 1 dose level until levels are satisfactory.
All Other	Other nonhematologic toxicity \geq Grade 3 felt related to dexamethasone	Hold dexamethasone dose. Resume at 1 dose decrement when toxicity has resolved to Grade 2 or less or to baseline. If toxicity recurs, discontinue dexamethasone permanently.

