- d) Allogeneic stem cell transplantation at least 24 weeks prior to starting KRT-232 (AMG 232) + KRd, and these subjects must also NOT have moderate to severe active acute or chronic graft versus host disease (GVHD).

3.1.6. Subjects must be ≥ 18 years old. Because no dosing or adverse event data are currently available on the use of KRT-232 (AMG 232) in combination with KRd, subjects < 18 years of age are excluded from this study.

3.1.7. Subjects must have ECOG performance status ≤ 2 (Karnofsky $\geq 60\%$, see Appendix A).

3.1.8. Subjects must have normal organ and marrow function as defined below:

- a) Absolute neutrophil count (ANC) $\geq 1,000/\text{mcL}$ without growth factors within 2 week of initiation of treatment
- b) Platelets $\geq 50,000 \text{ cells/mm}^3$ if marrow plasmacytosis $< 50\%$ OR platelet count $\geq 30,000 \text{ cells/mm}^3$ if marrow plasmacytosis $\geq 50\%$.
- c) Hemoglobin $\geq 8 \text{ g/dL}$ within 2 weeks of the initiation of treatment
- d) Total bilirubin $< 1.5 \times$ institutional upper limit of normal (ULN) ($< 2.0 \times$ ULN for subjects with documented Gilbert's syndrome or $< 3.0 \times$ ULN for subjects for whom the indirect bilirubin level suggests an extrahepatic source of elevation)
- e) AST(SGOT)/ALT(SGPT) $\leq 2.5 \times$ ULN
- f) Alkaline phosphatase $< 2.0 \times$ ULN (if liver or bone disease are present, $< 3.0 \times$ ULN)
- g) Creatinine clearance (eGFR) $\geq 50 \text{ mL/min}/1.73 \text{ m}^2$

3.1.9. Subjects must have adequate coagulation laboratory assessments, as follows:

Prothrombin time (PT) or partial thromboplastin time (PTT) $< 1.5 \times$ upper limit of normal (ULN), OR International normalized ratio (INR) < 1.5 .

3.1.10. Subjects who have received radiation therapy targeting $> 10\%$ of the bone marrow space must have completed this at least 2 weeks prior to starting therapy with KRT-232 (AMG 232) + KRd.

3.1.11. Subjects must be able and willing to provide bone marrow biopsies/aspirates and buccal swab as requested by the protocol.

3.1.12. Subjects must be willing to undergo myeloma genotyping for *TP53* mutation, insertion, or deletion at screening.

3.1.13. Subjects must have an estimated life expectancy of at least 3 months.

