5. TREATMENT PLAN

5.1. KRT-232 (AMG 232) + Carfilzomib, Lenalidomide, and Dexamethasone (KRd)

This will be a two-part Phase 1 dose-escalation and exploratory dose-expansion study of KRT-232 (AMG 232) in combination with carfilzomib, lenalidomide, and dexamethasone (KRd) in relapsed and/or refractory *TP53* WT myeloma subjects with 1-3 lines of prior therapy. Part A will consist of a dose-escalation phase of KRT-232 (AMG 232) to assess its safety and tolerability and identify an MTD/tentative RP2D in combination with KRd. KRT-232 (AMG 232) dose will be assigned according to the dose level stated in Section 5.4. Please refer to Section 5.4 to KRT-232 (AMG 232) dose escalation. After the MTD has been established, Part B of the study will involve an exploratory-dose expansion study of a goal of 10 additional subjects with relapsed and/or refractory myeloma who will be enrolled at the tentative RP2D.

Due to the timely need to initiate treatment in relapsed myeloma, *TP53* mutation status at screening is NOT required prior to KRT-232 (AMG 232) dosing. However, subjects found to have *TP53* mutation and/or deletion from screening bone marrow biopsy will be removed from study after C1 and continue on standard-of-care KRd alone. Toxicity monitoring of such subjects removed from active therapy with KRT-232 (AMG 232) will continue as described in the Treatment Plan. During the dose-expansion phase, subjects removed from study after Cycle 1 based on the *TP53* mutation and/or deletion status will be replaced to ensure that a goal of 10 subjects with *TP53* wild-type status are enrolled in the dose-expansion cohort.

Treatment will be administered on an outpatient basis. Reported adverse events and potential risks are described in Section 7. Appropriate dose modifications are described in Section 6. No investigational or commercial agents or therapies other than those described below may be administered with the intent to treat the subject's malignancy.

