5.4. KRT-232 (AMG 232) + Carfilzomib, Lenalidomide, and Dexamethasone Treatment Plan

Dose Regimen

KRT-232 (AMG 232) + carfilzomib, lenalidomide, and dexamethasone will be administered per the following schedule:

Cycles 1-12 (28 day cycle)

- KRT-232 (AMG 232) once daily by mouth 7 out of 28 days
- Carfilzomib 20 mg/m² IV on Days 1 and 2 of Cycle 1, escalating to 27 mg/m² IV on Days 8, 9, 15, 16 of Cycle 1 and continuing on Days 1, 2, 8, 9, 15, 16 of Cycles 2 through Cycle 12
- Lenalidomide 25 mg PO on Days 1-21
- Dexamethasone 40 mg PO or IV on Days 1, 8, 15, and 22

Cycles 13-18 (28 days each)

- KRT-232 (AMG 232) once daily by mouth 7 out of 28 days
- Carfilzomib 27 mg/m² IV on Days 1, 2, 15, and 16
- Lenalidomide 25 mg PO on Days 1-21
- Dexamethasone 40 mg PO or IV on Days 1, 8, 15, and 22

Cycles 19+ (28 days each)

- KRT-232 (AMG 232) once daily by mouth 7 out of 28 days
- Lenalidomide 25 mg PO on Days 1-21
- Dexamethasone 40 mg PO or IV on Days 1, 8, 15, and 22

Part A (Dose-escalation scheme)

The MTD is defined as the highest dose at which six subjects have been treated and less than two subjects experienced DLT within the first cycle of treatment in Phase I of the trial. To determine the MTD, escalation for KRT-232 (AMG 232) will be conducted following the “3+3” design with de-escalation. A cohort of three subjects will be treated at the starting dose level and observed until the end of the first cycle (subjects non-evaluable for DLT will be replaced). The dose level will be escalated with each new cohort until at least one out of three subjects of a cohort experiences DLT. If one subject experiences a DLT, then three additional subjects will be treated at the same dose level; if none of the three additional subjects experiences a DLT, then the dose escalation will be continued by treating the next cohort of three subjects at the next higher dose level. If at least two out of up to six subjects at a dose level experience a DLT, the MTD will be considered to have been exceeded, and up to 3 more subjects will be treated at the next lower dose if there are less than 6 subjects already treated at that dose. The dose steps for escalation are displayed below:

Dose Escalation Schedule	
Dose Level	Dose of KRT-232 (AMG 232)*
- 1	30 mg/day PO x 7 days out of 28 day cycle
+ 1	60 mg/day PO x 7 days out of 28 day cycle
+ 2	90 mg/day PO x 7 days out of 28 day cycle
+ 3	120 mg/day PO x 7 days out of 28 day cycle

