+ 4	180 mg/day PO x 7 days out of 28 day cycle
+ 5	240 mg/day PO x 7 days out of 28 day cycle

If dose-de-escalation is needed for Dose level 1, Dose level -1 is defined as 30 mg/day x 7 days out of 28 day cycle.

There should be no dose modifications of KRT-232 (AMG 232) and KRd during the DLT-evaluable period (Cycle 1). Subjects requiring dose-reductions during the DLT-evaluable period will be considered a DLT.

Part B (Dose-expansion scheme)

After determination of the KRT-232 (AMG 232) MTD or proven tolerability of the highest planned dose, and a goal of 10 additional subjects will be treated in the Part 2 dose expansion in combination with KRd. The primary objective of this dose-expansion phase is to confirm the safety and tolerability of KRT-232 (AMG 232) + KRd at the MTD and tentative RP2D in a goal

of 10 subjects with relapsed and/or refractory multiple myeloma. The tentative RP2D will be determined based on the review of safety data at the MTD.

During the dose-expansion phase, subjects removed from study after Cycle 1 based on the *TP53* mutation and/or deletion status will be replaced to ensure that a goal of 10 subjects with *TP53* wild-type status are enrolled in the dose-expansion cohort.

The subject will be requested to maintain a medication diary of each dose of medication. The medication diary will be returned to clinic staff at the end of each course.

KRT-232 (AMG 232)

The following medications and/or therapies should not be administered within the timeframes specified prior to enrollment and during the study (unless otherwise specified below):

- Antitumor therapy (chemotherapy, antibody therapy, molecular targeted therapy, retinoid therapy, hormonal therapy, or investigational agent) within 21 days of study day 1; concurrent use of hormone deprivation therapy for hormone-refractory prostate cancer or breast cancer and continuation of previous hormone therapy in breast cancer subjects are permitted.
- Treatment with immune modulators including, but not limited to, corticosteroids, cyclosporine and tacrolimus within 3 weeks prior to enrollment, except for a corticosteroid dose equivalent to dexamethasone of ≤ 4 mg/day
- Therapeutic or palliative radiation therapy within 4 weeks of KRT-232 (AMG 232) day 1.

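### Section 6.3 calls for reduced carfilzomib in baseline hepatic impairment, but the rule against Cycle 1 dose changes makes no exception for a starting dose set by a pre-treatment condition

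*Combined protocol and SAP*

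**What the plan says.** The carfilzomib guidance in Section 6.3 has a Hepatic Impairment row that opens with a "25% dose reduction in case of baseline or treatment emergent mild or moderate hepatic impairment". The later lines of that row cover withholding, restarting and monitoring.

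The head of Section 6 says: "There should be no dose modifications of KRT-232 (AMG 232) and KRD during the DLT-evaluable period (Cycle 1"). It continues: "Subjects requiring dose-reductions during the DLT-evaluable period (Cycle 1) will be considered a DLT". Section 5.4 carries the same pair of statements, the second as "Subjects requiring dose-reductions during the DLT-evaluable period will be considered a DLT", and the synopsis repeats them.

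The planned Cycle 1 regimen in Section 5.4 is "Carfilzomib 20 mg/m² IV on Days 1 and 2 of Cycle 1, escalating to 27 mg/m² IV on Days 8, 9, 15, 16". Section 5.3 gives the same single schedule, with no hepatic alternative. Section 5.1 adds: "Appropriate dose modifications are described in Section 6".

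On eligibility, Section 3.1.8 opens with "Subjects must have normal organ and marrow function as defined below". The limits it then sets allow AST/ALT up to 2.5 × ULN, bilirubin above ULN, and a higher alkaline phosphatase limit "if liver or bone disease are present". Section 6.6 includes withholding rules for subjects with underlying liver disease and abnormal transaminases at baseline.

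**The concern.** A baseline condition exists before the first infusion, so on its wording the 6.3 reduction applies from Cycle 1 Day 1. The Cycle 1 rule says the backbone should not be changed in that cycle and attaches a DLT to any subject who needs a reduction. Both are stated rules, and neither says which gives way.

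The practical risk is that two sites, each following the protocol in good faith, give different Cycle 1 carfilzomib to the same kind of subject. One site might give full dose to someone for whom the protocol states a safety reduction. Another might reduce the dose, and the subject would then enter the escalation decision with a below-plan backbone that the DLT listing does not show. On the literal wording, the reduction could also be scored as a DLT although nothing happened on treatment.

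The point concerns baseline impairment only. For impairment that emerges in Cycle 1, counting the reduction as a DLT is consistent with the rest of the plan.

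**Working it through.** **1. Do the rules meet in the same subject?** The 6.3 row is triggered by impairment at baseline or emerging on treatment. The Cycle 1 rule (synopsis, 5.4, head of Section 6) covers both KRT-232 and KRd and has no exception. Section 6.3 itself calls its action a dose reduction. An eligible subject with baseline impairment therefore falls under both.

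**2. Is that subject excluded?** Not by the text. Section 3.1.8 admits liver tests above normal, and 6.6 provides for abnormal baseline transaminases. However, mild or moderate hepatic impairment is defined nowhere in the documents, so the number affected cannot be computed.

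**3. Cycle 1 carfilzomib under each rule.** Inputs: infusions on Days 1, 2, 8, 9, 15 and 16, at 20 mg/m² for two doses and 27 mg/m² for four (5.4); dose levels of 27, 20 and 15 mg/m² (6.2); a 25% reduction (6.3).

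The 25% figure matches the 6.2 levels closely: 0.75 × 20 = 15 mg/m², and 0.75 × 27 = 20.25 mg/m², against a level of 20 mg/m².

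| Rule followed | Calculation | Planned Cycle 1 total |
|---|---|---|
| Section 6 / 5.4 (full dose) | 2 × 20 + 4 × 27 | 148 mg/m² |
| 6.3, exact 25% cut | 0.75 × 148 | 111 mg/m² |
| 6.3, using 6.2 levels | 2 × 15 + 4 × 20 | 110 mg/m² |

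- Following 6.3 gives less than plan: 148 − 111 = 37 mg/m² (37/148 = 25.0%) or 148 − 110 = 38 mg/m² (38/148 = 25.7%).
- Following Section 6 gives more than 6.3 allows: 37/111 = 33.3% or 38/110 = 34.5%, over six infusions.

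**4. Effect on a cohort's mean planned dose**, if one member is at 110 mg/m²:

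- Three subjects: (2 × 148 + 110)/3 = 135.3 mg/m², which is 8.6% lower.
- Six subjects: (5 × 148 + 110)/6 = 141.7 mg/m², which is 4.3% lower.

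**5. How the analysis rules treat that subject.** Section 13.1.4 decides DLT evaluability for a subject without a DLT from KRT-232 doses alone, so a subject on reduced carfilzomib stays evaluable. Section 13.2.1 lists DLTs by KRT-232 dose, so the listing would not show the reduced backbone.

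**6. Would the subject count as a DLT?** Section 5.6 defines a DLT as a treatment-emergent adverse event, and 13.2.2 requires the event to be new, re-emerging or worse than before treatment. A stable baseline condition meets none of these. The separate sentence on dose reductions is unqualified, though, and read alone it would count the subject.

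**The case against.** The strongest reply is that the conflict may have nobody to act on. Section 3.1.8 describes those who pass it as having normal organ function as it defines that, and raised transaminases or alkaline phosphatase are not the same as mild or moderate hepatic impairment. This stands as a limit on size: the affected number may be zero. It does not remove the conflict, because the 6.3 row provides for baseline impairment and the eligibility limits do not exclude it.

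Second, the wording is softer than an outright prohibition. The Cycle 1 rule says *should*, and 6.3 is headed as guidelines. A dose fixed before Day 1 is arguably not a modification made during Cycle 1. That is a sensible reading, but no text states it, and 6.3 uses the language of reduction.

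Third, Section 6 could govern Cycle 1, with the 6.3 row applying from Cycle 2. That reading is available, but it withholds a stated hepatic reduction for all six Cycle 1 infusions.

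Fourth, oversight limits harm. A coordinating-site designee approves each slot after documents including the latest clinic note are sent for review (4.3.2). There are at least monthly calls and Principal Investigator sign-off on escalation (12.1), and safety summaries are by treatment actually received (13.1.5). All of this helps, but none of it tells a site which dose to give on Day 1.

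A reader might also infer that the fixed doses in 5.4 are a second, separate conflict. They are not, because 5.1 refers to Section 6 for modifications.

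**Conclusion.** Wrong as written, and minor. Two stated rules give different Cycle 1 carfilzomib for a subject with baseline mild or moderate hepatic impairment: 148 mg/m² against 110–111 mg/m². The conclusion rests on such a subject being able to enrol, which the eligibility text permits but does not show to be likely.

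A reader might infer that false DLTs would stop escalation early. If one of the first three subjects counted as a DLT solely through this rule, the chance of escalating would be (1 − p)⁵ instead of (1 − p)³ + 3p(1 − p)⁵. At an assumed true DLT rate p of 20%, that is 0.328 against 0.709; at 10%, it is 0.590 against 0.906. The documents do not support relying on these figures. They give no true DLT rate for each dose level, they do not show that any such subject will enrol, and 5.6 with 13.2.2 makes the false-DLT reading the less natural one. No effect on MTD selection is shown. What stands is a risk of inconsistent dosing and, on the literal wording only, of a DLT counted for a baseline condition.

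**What to change.** Add a short clarification to the synopsis, Section 5.4 and the head of Section 6. It should say that a carfilzomib starting dose reduced before Cycle 1 Day 1 for baseline hepatic impairment under 6.3 (15 mg/m² on Days 1–2, then 20 mg/m²) is not a Cycle 1 dose modification and is not by itself a DLT, while any further reduction in Cycle 1 still is. Both doses are already levels in 6.2.

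State also that these subjects remain DLT-evaluable under 13.1.4, and flag them in the 13.2.1 DLT listing so that the reduced backbone is visible at escalation sign-off.

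If the sponsor intends 3.1.8 to exclude such subjects, delete *baseline* from the 6.3 row instead.

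The cost is a few words of protocol text and one listing flag, with no change to sample size, visits or procedures. The small downside of the first option is that a few cohort members may have below-plan carfilzomib while still informing the escalation decision; the flag makes that visible.
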